3.3.2.2 Quality of Life/Symptoms (Weeks 0, 4, 8, 12, 24, 36, 48*)

- Breathlessness
 - Extended MRC dyspnoea score (eMRC)
- Health Status
 - St George's Respiratory Questionnaire (SGRQ)
 - COPD Assessment Tool (CAT)
- Mental wellbeing
 - Warwick-Edinburgh Mental wellbeing score (WEMWBS)
- Functional
 - London Chest Activities of Daily Living Questionnaire (LCADL)

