4.6 Other Analysis Populations

N/A.

5 General Issues for Statistical Analysis

Continuous Outcome data with symmetric distribution will be described with summary statistics such as the mean and standard deviation (SD). Skewed continuous Outcome data will be described using the median and interquartile range (IQR). Determination of symmetry will be made informally by visualisation, taking into account sample size for each variable, the nature of potential outliers, and similarity between mean and median values (recognising formal statistics to test for normality often lead to spurious results).

Categorical Outcome data will be summarised with numbers (absolute frequency) and percentages.

Summary tables for both continuous and categorical outcome data will be presented by treatment group and overall in the intention to treat population.

For continuous outcomes that follow a normal distribution, we will compute the adjusted mean change from baseline for each treatment arm, presenting it alongside the corresponding 95% confidence interval.

For non-normally distributed continuous outcomes, and if transformations prove ineffective in enhancing normality, we will resort to a non-parametric approach—specifically, the Wilcoxon rank-sum test (Mann-Whitney two-sample statistic) to compare outcome values between the two treatment arms at each time point without applying baseline adjustments. The calculated statistics will include the median, interquartile range, as well as the minimum and maximum values for each treatment arm.

All time to event analyses will be accompanied by Kaplan-Meier survival curves to compare the survival rate between the two groups.

To visually represent non-normally distributed outcomes, we will create a whisker plot, illustrating the median along with the 25th and 75th percentiles, minimum, and maximum values for each treatment arm.

For visual representation of all other normally distributed continuous outcomes, line plots will be produced for the adjusted mean change from baseline in each treatment arm alongside a 95% confidence interval using time since randomisation on x-axis and adjusted mean change from baseline at y-axis.

5.1 *Derived/ Computed Variables*

Treatment allocation received

The reason for Protocol deviation concerning participants who received incorrect trial drug/placebo and the treatment allocation variables will be used to derive a binary

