6.5.1.2 Continuous Longitudinal Outcomes

All continuous longitudinal outcomes (repeated measurements) will be compared using mixed effects model with explanatory variables of treatment arm, stratification variables, visit number in weeks (categorical) and baseline value as fixed effects with participant identification as a random effect to account for repeated measures over time. This method will be able to handle missing data during the follow-up measurements. Adjusted mean differences alongside two sided 95% CI and P-value will be reported for these outcomes. Mean and standard deviation at baseline and over 48 weeks of the observed data will be presented by treatment arm. The adjusted mean change from baseline in each arm (with 95% confidence intervals) and the adjusted mean difference between groups (with 95% confidence intervals) will be presented alongside the 2-sided p-value from the model.

The model residuals corresponding to the continuous longitudinal outcomes will be assessed for normality by performing the Shapiro-Wilk Test.

Data will be assessed for the normality assumption using visualisation, taking into account sample size for each variable, the nature of potential outliers, and similarity between mean and median values (recognising formal statistics to test for normality

often lead to spurious results). If the distribution of the variable is found to be far from normally distributed, a log transformation will be used to modify the non-normality. In these cases adjusted geometric mean on the original scale (i.e. after anti-logging the result on the log scale) alongside standard errors on the log scale will be presented of the observed data. Geometric mean ratios from the model (with associated 95% CI and 2-sided p-value) will be reported to compare treatment groups.

Should a log transformation not correct for non-normally distributed data a non-parametric test such as the Mann Whitney U test can be utilised to assess the distribution of ranks between the treatment arms. Adjustment for other variables in the model including baseline value will not be possible and the Median (inter-quartile range), minimum, maximum of the observed data in each treatment arm will be presented along side the 2-sided p-value.

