Further analysis of the participant reported outcomes will be carried out assessing the treatment effect by visit. Mean and standard deviation (SD) in each treatment arm will be calculated at baseline and each follow-up time point for each outcome using the observed data.

A mixed effect model with dependent variable of the outcome at baseline and follow-up time points; explanatory variables of treatment arm, stratification variables, visit number in weeks (categorical), baseline value, and an interaction term between treatment and visit as fixed effects with participant identification as a random effect to account for repeated measures over time will be fitted for each outcome. Adjusted mean change from baseline in each treatment arm as well as adjusted mean difference between treatment arms at each time point with 95% confidence intervals and p-value will be reported.

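### The by-visit treatment differences for participant-reported outcomes rest on a participant random effect alone, which assumes equal variance and correlation from week 4 to week 48, so their intervals and p-values may be wrong.

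*SAP*

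**What the plan says.** SAP 6.5.1.2 contains two models.

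- **Main model.** The fixed effects are treatment, the stratification factors, and "visit number in weeks (categorical) and baseline value as fixed effects". The random part is "participant identification as a random effect to account for repeated measures over time". There is no treatment-by-visit term, so the result is one overall treatment effect.
- **By-visit model.** The SAP then adds: "Further analysis of the participant reported outcomes will be carried out assessing the treatment effect by visit". This model has "an interaction term between treatment and visit as fixed effects with participant identification as a random effect to account for repeated measures over time", and the "adjusted mean difference between treatment arms at each time point with 95% confidence intervals and p-value will be reported". Its response is described as follows: "A mixed effect model with dependent variable of the outcome at baseline and follow-up time points". Week 0 is therefore an outcome row, while the baseline value is also a covariate.

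Protocol 10.3.3 and SAP 6.5.1 likewise name only a patient random effect. Neither document states a residual covariance structure, a random slope, visit-specific variances or a type of standard error. The residual check listed in SAP 6.5.1.2 is for normality, not for variance or correlation across visits.

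For normally distributed continuous outcomes more generally, SAP section 5 says that "line plots will be produced for the adjusted mean change from baseline in each treatment arm alongside a 95% confidence interval". Those bars are per arm and carry no treatment p-value.

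**The concern.** A random intercept with independent residuals gives every visit the same residual variance. It also gives weeks 4 and 8 the same correlation as weeks 4 and 48. The schedule is uneven (weeks 4, 8, 12, 24, 36 and 48), and Protocol 7.6 places baseline within the admission or up to seven days after discharge. It is plausible that correlation weakens over such a year and that spread changes during recovery.

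If so, the model averages the variance over visits and applies that average to each one. Visits with above-average residual variance get intervals that are too narrow, and the others get intervals that are too wide. Week 48 also has the thinnest data, through truncated follow-up, death and withdrawal. SAP 5.2 makes no multiplicity correction. At stake are claims about when a benefit in the participant-reported scores appears and whether it lasts to week 48.

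**Working it through.** **The plan's own figure.** The only design figure is the sample size (SAP 2.2.3), and it reproduces.

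- Treated event probability: 1 − 0.35^0.6 = 0.4674.
- Events (Freedman): (1.96 + 0.8416)² × (1.6/0.4)² = 125.6, so 126.
- Mean event probability: (0.65 + 0.4674)/2 = 0.5587. Then 126/0.5587 = 225.5, so 226 (113 per arm), and 226/0.95 = 237.9, so 238.

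This says nothing about the longitudinal outcomes. Only the 113 per arm is carried forward.

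**Assumed inputs (not in the documents).** Raw SD is 1 at every visit. The correlation between visits is 0.25 + 0.6·exp(−gap in weeks/20). Data are complete and only post-baseline rows are used.

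**Step 1: correlation of each visit with baseline.** Weeks 4, 8, 12, 24, 36, 48: 0.7412, 0.6522, 0.5793, 0.4307, 0.3492, 0.3044. Under a random intercept the common baseline slope is their mean: b = 3.0570/6 = 0.5095.

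**Step 2: residual variance at visit t** = 1 + b² − 2b·r(t).

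- Week 4: 1.2596 − 0.7553 = 0.5043.
- Week 48: 1.2596 − 0.3102 = 0.9494.
- Average over visits: 1 − b² = 0.7404.

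Baseline adjustment alone makes the residual variance nearly double, although the raw SDs are equal.

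**Step 3: standard errors of the treatment difference.**

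- Model, every visit: √(2 × 0.7404/113) = 0.1145.
- True, week 4: √(2 × 0.5043/113) = 0.0945. Ratio model/true: 1.21.
- True, week 48: √(2 × 0.9494/113) = 0.1296. Ratio: 0.88.

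**Step 4: simulation, 1,500 trials, 113 per arm, same correlation.**

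| Scenario | SE ratio wk 4 | SE ratio wk 48 | Coverage wk 4 | Coverage wk 48 |
|---|---|---|---|---|
| Equal SDs, post-baseline rows | 1.21 | 0.89 | 98.3% | 90.8% |
| SD rising 0.8 to 1.2, post-baseline rows | 1.67 | 0.79 | 100% | 87.9% |
| Equal SDs, week-0 row included | 1.20 | 0.83 | 98.0% | 90.0% |
| SD rising 0.8 to 1.2, week-0 row included | 1.57 | 0.70 | 99.8% | 83.5% |

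The first row agrees with the hand calculation. Including week 0, as the SAP describes, worsens week 48, because the week-0 residual variance is far smaller and pulls the average down.

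**Step 5: with missing data.** A further simulation with 113 per arm, 30% missing by week 48, assumed decaying correlation and equal SDs gave a week-48 ratio of 0.79-0.89. The false-positive rate was 8-13%, against about 7% with cluster-robust standard errors.

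**Step 6: where there is no error, or the opposite error.**

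- True compound symmetry: ratio 1.00 and coverage 95% at every visit.
- Decaying correlation, equal SDs, complete data and no baseline adjustment: 1.00 at every visit. Decay acts through baseline adjustment and missing data. With retention falling to 45% and still no adjustment, the week-48 ratio is 0.91.
- SD falling 1.2 to 0.8, with correlation 0.5 + 0.3·exp(−gap/12): week-48 ratio 1.07 and 4% rejections, so slightly conservative.
- Overall effect without the visit interaction: ratio 1.00 in every large-sample scenario (missingness unrelated to outcome).

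**Step 7: can an unstructured covariance simply be added?** Not to the by-visit model as described. With week 0 as both outcome and covariate, a baseline slope of 1 fits that row exactly and its residual variance goes to zero. In a check with 119 per arm the log-likelihood was 862 at slope 0, 1958 at 0.99 and 4151 at 0.999999, rising without bound. The week-0 row has to go first.

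**The case against.** The SAP nowhere says that the random part is an intercept only, that residuals are independent, or that standard errors are model-based. That is fair: these are the plain reading of a plan that names one random effect and nothing else. If something else is intended, stating it settles the point.

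A reader might infer that all the longitudinal results are affected. The documents do not support that. By-visit treatment contrasts appear only in the additional analysis of participant-reported outcomes. Handgrip strength, SPPB and eosinophil counts get the single overall effect, whose standard error held in these calculations.

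A reader might also infer that late intervals are always too narrow. Nothing in the documents fixes the direction, since they give no SD, correlation or missingness figure and the falling-SD case went the other way.

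Finally, these are secondary p-values without multiplicity control, so the consequence is limited. That stands, and it keeps this a low-priority improvement. It does not remove the case for it: by-visit intervals and p-values are promised, and a better-suited model is readily available.

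**Conclusion.** The point holds for the by-visit model in SAP 6.5.1.2. As written, its intervals and p-values depend on compound symmetry, which is doubtful over an uneven year of follow-up with baseline adjustment. Under assumed decaying correlation and equal SDs, the week-48 standard error is roughly 10-20% too small, the false-positive rate is about 8-13%, and the week-4 standard error is too large. These sizes rest wholly on assumed SDs, correlations and missingness. The error can be nil or reversed.

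The overall effect, the primary Cox analysis and the 226/238 sample size are not materially affected. One matter was not computed: whether missingness that depends on earlier outcomes would bias the estimates under a wrong covariance.

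**What to change.** In the by-visit model of SAP 6.5.1.2:

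1. Remove week 0 from the outcome rows. Keep baseline as a covariate and add a baseline-by-visit term.
2. Replace the participant random effect with an unstructured residual covariance over weeks 4, 8, 12, 24, 36 and 48, with small-sample degrees of freedom.
3. State how truncated participants' final assessments are assigned to a visit. Protocol 4.1 steps the final visit down from week 44 to 40 and so on to a minimum of 24. Weeks 44, 40, 32 and 28 are not scheduled outcome visits.
4. Name the fallback: if the model does not converge, keep the participant random intercept with standard errors clustered by participant.

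The cost is a few sentences and a model option. No new data are needed, and the SAP introduction provides for amendment before database lock. The drawback is 6 × 7/2 = 21 covariance parameters and possible non-convergence, which the fallback covers. The simulations tested the cluster-robust fallback. The unstructured fit was examined only in the large-sample calculation.

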The time from randomisation to next hospital readmission (respiratory cause) is defined as a time to event outcome measured in days. The date of randomisation and the date of next hospital readmission (respiratory cause) will be used to calculate time to event. Where hospital readmission for respiratory cause doesn't occur during follow-up, time will be measured until the participant's last known follow-up assessment. A variable to indicate event (with a value of 1) or no event (with a value of 0) will be derived.

- Time to discharge from index admission

Time to discharge from index admission is a continuous outcome defined as the time (measured in days) from index admission to discharge. The date of index admission and the date of hospital discharge will be used to calculate length in days and the resulting index admission duration, expressed in days, will be incorporated into the baseline characteristics for analysis and reporting. Participants with a date of death and no discharge date will not have a value for length of index admission and therefore not included in the analysis of this outcome measure.

Quality of Life/Symptoms (Weeks 0, 4, 8, 12, 24, 36, 48*)

*See section 1.2 – Truncated follow-up; Participants randomised from June 2023 will receive minimum 24 weeks follow-up.

- Breathlessness:
 - Extended MRC dyspnoea score (eMRC)

The extended MRC dyspnoea scale is defined as an ordinal outcome. It consists of five statements about a perceived grade of breathlessness related to activity, with the grades defined as shown below:

- Grade 1: Breathless only with strenuous exercise.
- Grade 2: Breathless when hurrying on the level or walking up a slight hill.
- Grade 3: Walks slower than peers or stops when walking on the flat at own pace.
- Grade 4: Stops after walking 100m, or for a few minutes, on the level.
- Grade 5: Too breathless to leave the house.

For participants who perceive themselves to be in a Grade 5 on the traditional MRCD scale, the eMRCD will categorise them as either 5a or 5b depending on their ability to manage personal care (i.e. washing and dressing) (Nerys, W.,2017; Steer J. et al, 2011).

The baseline value used in analysis should be the stable state value captured at baseline post randomisation, the actually value taken at baseline during the exacerbated state is for describing baseline characteristics only.

- Health Status
 - St George's Respiratory Questionnaire (SGRQ)
 - COPD Assessment Tool (CAT)

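### The by-visit model for participant-reported outcomes uses baseline both as outcome and as covariate, so its visit-level standard errors are about 4–7% too small and its change-from-baseline contrast is unadjusted

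*SAP*

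**What the plan says.** SAP 6.5.1.2 contains two mixed models for continuous repeated measures.

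- **Main longitudinal model.** Its fixed effects are treatment arm, the stratification variables, "visit number in weeks (categorical) and baseline value as fixed effects with participant identification as a random effect". Baseline is a covariate here and is not said to be a value of the dependent variable.
- **By-visit model.** It is introduced as follows: "Further analysis of the participant reported outcomes will be carried out assessing the treatment effect by visit". The model is "A mixed effect model with dependent variable of the outcome at baseline and follow-up time points; explanatory variables of treatment arm", followed by the stratification variables, categorical visit, "baseline value, and an interaction term between treatment and visit as fixed effects". The participant enters through a random term. The reported output is "Adjusted mean change from baseline in each treatment arm as well as adjusted mean difference between treatment arms at each time point", with confidence intervals and p-values.

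The continuous participant-reported scores are SGRQ, CAT, WEMWBS and LCADL, measured at baseline and at six follow-up visits (SAP 3.2.1), or fewer for some participants on truncated follow-up. No residual covariance structure is named. Nothing in the SAP removes the covariate from the week-0 row, gives baseline a visit-specific slope, or constrains the arms to be equal at baseline. SAP 6.2 rules out significance tests and confidence intervals for baseline differences between the arms.

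**The concern.** Baseline can be handled as a covariate or as part of the outcome vector. The by-visit sentence does both. In the week-0 row the response is predicted by itself, which has two consequences.

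1. The single baseline slope is pulled towards 1, and the week-0 residuals are smaller than those at follow-up. If residual variance is pooled over visits, the follow-up visits are given an error variance that is too small.
2. The same slope applies at week 0 and at follow-up, so any contrast of a follow-up visit against week 0 removes the covariate.

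At stake are the stated precision of the visit-level treatment effects on four quality-of-life and function scores, and whether changes labelled as adjusted are adjusted for baseline. SGRQ is one of the outcomes that SAP 6.5.3 treats as key secondary outcomes. Read literally, a difference at each time point also produces a between-arm p-value at week 0, which conflicts with SAP 6.2.

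**Working it through.** The plan states no figure for this analysis, so there is nothing of its own to reproduce first.

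**Inputs.** From the SAP: K = 6 follow-ups, one baseline slope, treatment-by-visit terms and a participant random effect. Assumed, because the documents are silent: random intercept with equal residual variance, complete data, unit variance at every visit, and the same correlation r between all pairs of visits, with r from 0.3 to 0.8.

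**1. Between-arm difference at a follow-up visit**

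- Fitted slope: b = (1 + K·r)/(K + 1). With follow-up rows only it would be r.
- Residual variance at week 0: (1 − b)². At follow-up: 1 − 2br + b². Their average over the K + 1 rows simplifies to 1 − b², which is what the model uses.
- Model SE / true SE = √[(1 − b²)/(1 − 2br + b²)]. Type I error = 2Φ(−1.96 × ratio).

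At r = 0.5: b = (1 + 3)/7 = 0.571; week-0 residual variance 0.429² = 0.184; follow-up 1 − 0.571 + 0.327 = 0.755; model value 1 − 0.327 = 0.673. The ratio is √(0.673/0.755) = 0.944.

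| r | b | 1 − b² | 1 − 2br + b² | SE ratio | Type I error |
|---|---|---|---|---|---|
| 0.3 | 0.400 | 0.840 | 0.920 | 0.956 | 6.1% |
| 0.5 | 0.571 | 0.673 | 0.755 | 0.944 | 6.4% |
| 0.7 | 0.743 | 0.448 | 0.512 | 0.936 | 6.7% |
| 0.8 | 0.829 | 0.313 | 0.361 | 0.932 | 6.8% |

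**2. Between-arm difference in change from baseline**

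Let D₀ and Dₖ be the raw between-arm differences at week 0 and at visit k. With complete data the model's differences are (1 − b)D₀ at week 0 and Dₖ − bD₀ at visit k. Subtracting gives Dₖ − D₀, the raw difference in mean change, whatever b is. On one simulated complete data set the estimate was −0.02756 with SE 0.12997, both with and without the covariate.

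The variance of a change score is 2(1 − r), against 1 − r² for ANCOVA, so the SE ratio is √[2/(1 + r)]: 1.24, 1.15 and 1.08 at r = 0.3, 0.5 and 0.7.

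**3. Simulation check**

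Null trials with 226 patients, six follow-ups, REML random intercept, stratification factors omitted, 8,000 trials per row. Entries are model SE / true SE, then type I error, at week 48.

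| Scenario | Visit difference, as written | Visit difference, post-baseline rows only | Change contrast, as written |
|---|---|---|---|
| r = 0.5, complete | 0.937; 6.8% | 0.992; 5.3% | 0.992; 5.2% |
| r = 0.7, complete | 0.933; 6.8% | 0.996; 5.1% | 0.997; 5.2% |
| r = 0.5, 30% dropout | 0.954; 6.0% | 1.013; 4.5% | 1.009; 4.8% |

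A separate run of 8,000 trials at r = 0.5 gave 0.956 and 6.1% as written, and 1.01 and 5.0% with post-baseline rows only. The Monte Carlo error of a 6.4% rate is √(0.064 × 0.936/8000) = 0.3 percentage points, so the two runs bracket the closed-form 6.4%.

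**The case against.** The strongest reply is about reach. This is a further analysis of secondary outcomes. The main model for the same scores uses baseline only as a covariate, and the primary analysis is a Cox model. The change-from-baseline comparison is unbiased under randomisation, and the arm-by-arm changes are named first among the outputs. The equal-variance assumption is the usual default, not stated text. All of this stands and limits the point.

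The authors may also have meant only that baseline data enter the analysis. The sentence does not say that, and a programmer would code it as written. A more flexible covariance is no rescue: if it were unstructured, a slope of exactly 1 would make every week-0 residual zero and the likelihood unbounded.

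A reader might infer three stronger things that the documents do not support.

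- **That the change-from-baseline intervals are also too narrow.** Under exchangeable correlation they are not (ratio 0.99 to 1.01). They would be if baseline correlated less with follow-up than follow-ups do with each other. At an assumed 0.4 against 0.7, the ratio is 0.80 and type I error 11.9%. That pattern is plausible around an acute admission, but the documents report no correlations.
- **That truncated follow-up makes the error much worse.** Four follow-ups for everyone would give ratios of 0.93 to 0.90 and type I error of 6.8 to 7.7%. Under SAP 2.1, however, July and August 2023 recruits still have six follow-up assessments, September to November recruits five, and only December recruits four, and all enter one pooled model.
- **That the week-0 row has almost no residual variance.** At r = 0.5 it has 0.184/0.755, about a quarter of the follow-up value.

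**Conclusion.** The by-visit model is wrong as written, and nothing elsewhere in the SAP corrects it. The two effects fall on different contrasts and should be kept apart.

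- **Difference at a follow-up visit:** overstated precision, of modest size.
- **Difference in change from baseline:** a valid standard error, but no benefit from the baseline adjustment. It also disagrees with the visit difference from the same model by (1 − b)D₀, so the two outputs will not reconcile whenever the arms differ by chance at baseline.

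The sizes rest on the assumed random intercept, equal variances, complete data and exchangeable correlation. The direction of the first effect and the cancellation in the second follow from the algebra under that structure. The correction is worth making before the SAP is finalised. It does not call into question the primary result, the sample size or the main longitudinal estimates as worded.

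**What to change.** Rewrite the by-visit sentence in one of two ways.

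1. **Post-baseline outcome (simpler).** Make the dependent variable the score at weeks 4, 8, 12, 24, 36 and 48 or final follow-up. Keep baseline value, stratification factors, visit and treatment-by-visit as fixed effects. Obtain each arm's change from baseline by subtracting the overall baseline mean from the adjusted visit mean.
2. **Constrained longitudinal model.** Keep baseline in the outcome vector, drop the baseline covariate and constrain the arms to a common baseline mean. Use a covariance structure that does not force the baseline-to-follow-up correlation to equal the correlation among follow-ups.

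In either case, name the covariance structure and limit between-arm differences and p-values to post-baseline visits, which removes the conflict with SAP 6.2.

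The cost is one SAP sentence and, for the first option, a filter in the code; no new data are needed. Intervals for the visit differences become slightly wider. Under the first option the factor is √[(1 − r²)/(1 − b²)], which is √(0.91/0.840) = 1.04 at r = 0.3 and √(0.36/0.313) = 1.07 at r = 0.8.
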